3.0 Background

- 3.1 During thoracic surgery, specific anesthetic techniques are used to isolate the lungs and allow for single-lung ventilation (SLV) so that the ipsilateral lung is not ventilated during the surgical procedure.¹⁻³ A motionless lung on the side of surgery is necessary to allow for the surgical procedure to proceed optimally. To accomplish SLV, there are several options including use of a specialized double-lumen

PROTOCOL TITLE: Ultrasound to verify lung-isolation during single-lung ventilation

endotracheal tube (DLT), placement of a bronchial blocker into the main stem bronchus of the operative side, or selective main stem intubation with a standard endotracheal tube (ETT). All of these devices allow for selective ventilation of the non-operative lung. In common clinical practice, the placement of the device for SLV may be guided by direct vision using a fiberoptic bronchoscope (FOB) and/or differential auscultation of the two lungs.

More recently, there has been increased use of ultrasonography at the bedside in various clinical locations including the Pediatric ICU and the operating room. Ultrasonography is painless, non-invasive and carries no risk. Given its ease of use and non-invasive nature, ultrasound is being used more frequently to make thoracic diagnoses including hemothorax, pneumothorax, pneumonia, and ARDS.³⁻⁸ More recently, preliminary data from three studies in adults suggest that ultrasound can be used to confirm lung isolation during SLV.⁹⁻¹¹ When the lung is not ventilated, there is no pleural movement noted (absence of lung sliding and no B-lines) and as the lung is non-mobile, the cardiac impulses may be transmitted through the lung to the chest wall and can be seen (presence of lung pulse). To date, there is only one anecdotal report of the intraoperative use of thoracic ultrasonography in the pediatric-aged patient.¹² The purpose of the current study is to prospectively evaluate the usefulness of thoracic ultrasonography in demonstrating effective lung isolation during SLV in the pediatric patient. Our primary hypothesis is that ultrasound will accurately verify lung separation during SLV, as compared to FOB.

- 3.2 This would provide a rapid and non-invasive means to demonstrate effective lung isolation without the time, cost, and invasive nature of direct visualization using a FOB.

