6.0 Procedures Involved*

PROTOCOL TITLE: Ultrasound to verify lung-isolation during single-lung ventilation

6.1 The proposed study will be conducted in 80 patients, ranging in age from 0 to 21 years. There will be no change in clinical practice regarding choice of anesthetic technique including premedication, device used for SLV, monitoring, induction, and maintenance of anesthesia. An investigator will identify patients in whom SLV is required for thoracic surgery. There will be total of three anesthesia providers and one surgeon involved in the study. One will be the primary anesthesiologist, who is one of the attending faculty and will be responsible for patient care during the perioperative period. They will decide prior to and during the case whether the patient is appropriate for and able to complete the study protocol. The other two anesthesia providers will be members of the study team or other anesthesia attending/fellow and will include an auscultator (may be a resident/CRNA/SRNA), the anesthesia provider who will perform the auscultation examination and the ultrasonographer, the anesthesia provider who will perform the ultrasound examination (see below). The surgeon will be the attending surgeon and will confirm the efficacy of one-lung ventilation during the surgical procedure. Both the auscultator and ultrasonographer will be blinded to the lung that is isolated.

The technique of SLV will be determined by the attending anesthesiology to include a DLT, bronchial blocker or main stem intubation with an ETT. The ventilator settings will be standardized until all of the study measurements and data have been collected:

Ventilation Mode: PRVC

RR titrated to achieve normocapnia

Inspiratory time 1 second

TV set at 6-8 ml/kg

PEEP: minimum of 5 cm H20

100% FiO2

6.2 After anesthetic induction the following ventilatory parameters will be recorded: tidal volume, peak inflating pressure, inspiratory time, respiratory rate, inspired oxygen concentration, end-tidal carbon dioxide, and oxygen saturation. After placement of the device for SLV, and isolation of the lung, the non-operative lung will be ventilated and the ventilatory parameters will be recorded again. Clinical confirmation of effective lung separation will include auscultation with documentation of absence of breath sounds on the operative side. Following this, correct placement of the DLT will be confirmed using FOB. The time to perform FOB will be determined.

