6.3 Once SLV device placement is confirmed by bronchoscopy, the patient's face and airway management devices will be covered by a drape to blind to auscultator and ultrasonographer. The auscultator

PROTOCOL TITLE: Ultrasound to verify lung-isolation during single-lung ventilation

and ultrasonographer will then enter the room. The auscultator will evaluate lung isolation and note the results. The ultrasonographer will then evaluate lung isolation with absence of lung sliding and the presence of lung pulse on the operative (non-ventilated) lung, and B-line. The procedure time for each (auscultation and ultrasonography) will be determined. Procedure time will be calculated from the time that the participant touches the patient to the completion of the examination (auscultation or ultrasonography). After the completion of the ultrasound examination, the patient will be placed in the surgical position. Following this, the surgical procedure will be started and lung separation documented by the surgeon. If lung separation was not successful, this will be noted. The intraoperative ventilation strategy will be at the discretion of the attending anesthesiologist.

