10.0 Inclusion and Exclusion Criteria*

10.1 Potential subjects will be identified by reviewing the surgery schedule in Epic and will be recruited from the Surgery Unit pre-op area prior to their surgery.

10.2 Inclusion criteria: Age 0-21 years, requiring SLV for thoracic surgery.

Exclusion criteria: None.

10.3 We are including children, and will not include:

- Adults unable to consent
- Pregnant women
- Prisoners

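### Examiners are to be blinded to the isolated lung, but that lung is always the operative one and no stated measure conceals the surgical side

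*Combined protocol and SAP*

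**What the plan says.** Section 6.1 sets the rule: "Both the auscultator and ultrasonographer will be blinded to the lung that is isolated". Section 6.3 gives the means. After bronchoscopic confirmation, the face and "airway management devices will be covered by a drape to blind to auscultator and ultrasonographer"; the auscultator "and ultrasonographer will then enter the room" only at that point. Surgical positioning comes after the ultrasound, so posture does not reveal the side.

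The lung to be isolated is fixed by the operation. Section 3.1 explains that single-lung ventilation is used "so that the ipsilateral lung is not ventilated during the surgical procedure", and section 6.2 states that after isolation "the non-operative lung will be ventilated". No patient has a random or sham side.

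Section 6.3 describes the ultrasound assessment as absence of lung sliding and "the presence of lung pulse on the operative (non-ventilated) lung, and B-line". Endpoint 4.1 covers both lung fields but also labels them operative and non-operative. No left/right response is defined for either examiner.

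On who may know the side: section 6.1 lets the examiners be study-team members or other anesthesia staff and has an investigator identify patients. Section 10.1 adds "Potential subjects will be identified by reviewing the surgery schedule in Epic". Section 25.1 gives enrolment to research coordinators and associates.

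**The concern.** Because the intended isolated lung and the operative lung are the same in every patient, blinding to one requires blinding to the other. The drape, the late entry and the late positioning hide the device and the posture. None of them hides which side is to be operated on. The wording of 6.3 sits badly with 6.1, because an examiner who follows it literally has to be told which lung is operative.

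The primary endpoint is the accuracy of a judgement made by a person. Examinations start only after bronchoscopic confirmation, so most examined patients should be truly isolated, and an examiner who knows the side has a strong prior answer. The hypothesis in 2.2 is accuracy of at least 80% for ultrasound, and greater than for auscultation. Both parts are open to expectation bias if calls rest partly on prior knowledge.

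**Working it through.** **The plan's own figure.** Section 12.2 claims more than 80% power with 80 patients, accuracy 85% and a 10-point difference, two-tailed. Taking 85% against 95% with alpha 0.05 (alpha is not stated, so assumed):

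- Null standard error: √(0.85 × 0.15 / 80) = 0.0399; times 1.96 = 0.0782.
- Alternative standard error: √(0.95 × 0.05 / 80) = 0.0244.
- Power = Φ((0.10 − 0.0782) / 0.0244) ≈ 81.4%.

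The figure reproduces on that reading, and this concern does not affect it. What is affected is the accuracy estimate itself.

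**Inputs for the bias.**

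- Target 80% (section 2.2).
- a, accuracy when the examiner relies on the examination alone: not known; 70% and 75% used as assumptions.
- k, share of examinations answered from knowledge of the side: not in the documents; 20% and 40% assumed.
- s, share of examined patients truly isolated: not in the documents; 90% to 100% assumed, since examinations follow bronchoscopic confirmation.

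**Formula.** A call made from knowledge of the side is right when the intended lung is in fact isolated, so observed accuracy = k·s + (1−k)·a.

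| a | k | s = 90% | s = 100% |
|---|---|---|---|
| 75% | 20% | 0.18 + 0.60 = 78% | 0.20 + 0.60 = 80% |
| 75% | 40% | 0.36 + 0.45 = 81% | 0.40 + 0.45 = 85% |
| 70% | 40% | 0.36 + 0.42 = 78% | 0.40 + 0.42 = 82% |

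**Leakage needed to reach the target.** Setting the formula to 0.80 gives k = (0.80 − a) / (s − a). For a = 75% this is 0.05 / 0.25 = 20% at s = 100%, and 0.05 / 0.15 = 33% at s = 90%.

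**Effect on ultrasound versus auscultation (s = 100%).**

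- Equal leakage shrinks the difference by the factor (1−k). With true accuracies 85% and 70% and k = 40%: 0.40 + 0.60 × 0.85 = 91%, and 0.40 + 0.60 × 0.70 = 82%. Fifteen points become nine.
- Unequal leakage can create a difference. With both true accuracies 75%, k = 40% for one examiner and 0 for the other gives 85% against 75%. The ten points favour whichever examiner knew the side.

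**The case against.** The plan does more than drape the patient: late entry and late positioning are real safeguards. Section 6.1 is itself a rule, and an examiner who knows the side arguably breaches it. Enrolment is assigned in 25.1 to staff who are not described as examiners, which weakens the consent route. All of this stands. It narrows the gap to a missing method of concealing the side, but does not close it, since 6.1 has an investigator identifying patients and allows study-team members to examine.

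A reader might infer four stronger things that the documents do not support.

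- *That 6.3 flatly contradicts 6.1.* The phrase "the presence of lung pulse on the operative (non-ventilated) lung" can be read as defining a positive scan for the protocol's reader, with both fields scanned under 4.1 and the operative label attached afterwards. The wording needs reconciling on either reading, but it does not say that the examiner is told the side.
- *That the examiners will know the side.* No section says so. Nor do the documents say that the surgery schedule shows laterality.
- *That knowing the side makes the call correct whatever the image shows.* It identifies the intended lung and does not prove isolation; 6.3 itself provides for separation that fails. This is why s is in the formula.
- *That the bias favours ultrasound.* Nothing says that ultrasonographers know the side more often than auscultators, and equal leakage works against the superiority hypothesis.

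**Conclusion.** The concern holds in a conditional form. The plan promises blinding to the isolated lung, gives no means of concealing the surgical side that determines it, and words the ultrasound task by the operative lung. The primary accuracy estimate is therefore open to expectation bias that the plan neither prevents nor records.

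The size depends on assumed values. With blinded accuracy 75% and 40% of calls made from knowledge of the side, observed accuracy is 81% to 85% for s between 90% and 100%, against a target of 80%. Smaller leakage, or lower s, may leave the result below the target, as the 78% entries show. The effect on the paired comparison has no predictable direction. This is a worthwhile, inexpensive improvement to the primary endpoint; the material does not show that the study's result would be invalid.

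**What to change.** 1. In 6.3, replace the operative-lung wording with: *each examiner assesses right then left in fixed order and records which lung is isolated (left / right / both / neither / indeterminate) before any unblinding*. Attach the operative label at analysis.
2. In 6.1, add: *the examiners for a patient have not identified or consented that patient, and have not reviewed the schedule or chart for the surgical side*.
3. Add one form item in which each examiner records whether they knew the surgical side.
4. In 17.1, add a sensitivity analysis that repeats the primary analysis without the examinations where the side was known. For the paired comparison, this means dropping the pair.

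The cost is protocol wording, one form item, a small scheduling limit on who examines which patient, and a smaller sample in the sensitivity analysis. No extra staff are needed and patient care is unchanged. The form item has to be in place when the examinations are done, because knowledge of the side cannot be recovered reliably afterwards.

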2.0 Objectives

- 2.1 The primary objective is to determine the accuracy of auscultation and ultrasonography for confirming lung isolation during SLV, as compared to direct visualization using FOB (gold standard). The secondary objective is to compare the time required to confirm lung isolation using the above-mentioned techniques including auscultation, FOB, and ultrasound.
- 2.2 The hypothesis is that ultrasonography will have at least 80% accuracy for verifying lung separation during SLV as confirmed by FOB; and will have greater accuracy than auscultation.

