5.0 Study Intervention/Investigational Agent

- 5.1 The only intervention being used that is not normally used in general clinical practice is the use of ultrasonography. The technique is non-invasive and poses no risk. Ultrasonography will be performed by an anesthesiologist with training and experience and will add less than 10 minutes to the anesthetic time.

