17.0 Data Management* and Confidentiality

17.1 We will compare the accuracy, sensitivity, and specificity of ultrasonography and auscultation (using FOB confirmation of one-lung isolation as the reference standard) using paired tests of proportions. As a secondary, exploratory aim, we will compare the time to perform each of the techniques using paired t-tests or sign-rank tests (according to the normality of the outcome distribution).

17.2 Research records will be stored in a locked cabinet and password protected computer. Only certified research personnel will be given access to identifiable subject information

17.3 Following publication of study results, research records will be stored for a period of 3-5 years and then will be destroyed by placing in a secure shredding bin.

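### Auscultation always precedes ultrasound after a single earlier bronchoscopy, so the paired accuracy difference cannot be separated from a possible, unmeasured order or time effect

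*Combined protocol and SAP*

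**What the plan says.** Section 6.2 describes one FOB step, after a clinical auscultation: "Following this, correct placement of the DLT will be confirmed using FOB". Section 6.3 continues: "Once SLV device placement is confirmed by bronchoscopy, the patient's face and airway management devices will be covered by a drape". Both examiners then enter, and the order of the study examinations is the same for all 80 patients: "The auscultator will evaluate lung isolation and note the results. The ultrasonographer will then evaluate lung isolation". No repeat FOB and no randomised or alternating order is described. Section 6.3 times each examination from first touch to completion. That gives durations, but not the clock times of isolation, FOB or examination start.

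Section 17.1 compares accuracy, sensitivity and specificity of the two techniques against FOB "using paired tests of proportions". Section 2.2 has two parts: ultrasound is at least 80% accurate, and it "will have greater accuracy than auscultation".

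Three provisions bear on stability between the examinations. Section 6.1: "The ventilator settings will be standardized until all of the study measurements and data have been collected". Section 6.3: "After the completion of the ultrasound examination, the patient will be placed in the surgical position". Section 5.1 says that ultrasonography "will add less than 10 minutes to the anesthetic time".

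**The concern.** Each patient is examined twice, in two successive periods, but only one sequence is used. Ultrasound is always the second look, later after isolation and further from the FOB reference than auscultation. If the state of the lung or device changes in between, the change falls on ultrasound alone, and a paired test counts it as a difference between techniques. With a single sequence no analysis can separate the two. Without clock times, the result cannot even be related to the interval.

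The second part of the hypothesis is at stake, because it rests entirely on this paired difference. The sign could go either way. Isolation lost after FOB would penalise ultrasound. Isolation that becomes easier to detect with time would favour it.

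**Working it through.** **The plan's own figure.** Section 12.2 states more than 80% power for a two-tailed one-sample test with 80 patients, 85% accuracy and a 10-point difference. Alpha is not stated; I take 0.05. With the null variance in the critical value, and 0.85 against 0.95:

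power = Φ[(0.10 × √80 − 1.96 × √(0.85 × 0.15)) / √(0.95 × 0.05)] = Φ[(0.894 − 0.700) / 0.218] = Φ(0.89) = 81.4%.

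The figure reproduces on that reading. It is a one-sample calculation, so it neither covers nor depends on the paired comparison discussed here.

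**Inputs.** N = 80 and accuracy A = 0.85 come from section 12.2. Assumptions that are not in the documents: both techniques have the same accuracy, their errors are independent, and isolation status changes between the first and second examination in a share f of patients.

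**Size of the shift.** The second examination is scored against the earlier FOB. Where status has changed, a correct reading of the current state counts as wrong, and the reverse:

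observed accuracy of the second test = A(1 − f) + (1 − A)f = A − f(2A − 1).

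The spurious ultrasound-minus-auscultation difference is therefore −f(2A − 1). At A = 0.85, 2A − 1 = 0.70. The rejection rates below are simulated (20,000 trials per row, no true difference between techniques). Section 17.1 does not name the version of the paired test, so both versions of McNemar's test are shown.

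| Order | f | Patients of 80 | Shift (points) | Asymptotic McNemar | Exact McNemar |
|---|---|---|---|---|---|
| Fixed | 0 | 0 | 0 | 5.1% | 2.8% |
| Fixed | 2% | 1.6 | −1.4 | 6.3% | 3.6% |
| Fixed | 5% | 4 | −3.5 | 9.5% | 5.8% |
| Fixed | 10% | 8 | −7.0 | 21.0% | 14.5% |
| Randomised | 5% | 4 | about 0 | 5.1% | 2.7% |
| Randomised | 10% | 8 | about 0 | 5.1% | 2.9% |

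At f = 5% the shift is −2.5 points if A = 0.75 and −4.5 points if A = 0.95. An artefact of 10 points at A = 0.85 needs f = 0.10/0.70 = 14%, about 11 of 80 patients.

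**Why randomising helps.** In half the patients ultrasound comes second and in half auscultation does, so the expected shift is −½f(2A − 1) + ½f(2A − 1) = 0.

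**What the model leaves out.** The negative sign belongs to a change of status scored against an old reference. If status is stable but detectability improves with time, the shift is positive. The documents give no figure for that either.

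**The case against.** The strongest reply is that aliasing alone is not bias. Something must change between two consecutive examinations, and the protocol leaves little room for that. Ventilator settings are standardised until data collection ends, the patient is repositioned only afterwards, ultrasound adds less than 10 minutes, and section 9.0 puts total participation at 15–30 minutes. Draping and the examiners' entry precede both tests, so any disturbance from them reaches both; only the auscultation itself lies between. All of this stands, and it makes a small f plausible. It does not establish one: the ventilator provisions include ranges and targets, and the interval from FOB to each examination is not recorded. The surgeon's later check follows repositioning and is not a reference in section 17.1, so it cannot show the state at either examination.

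A reader might infer that the paired difference cannot be attributed to technique at all. The documents do not support that. They show a possible effect of unknown size, and at f up to about 2% the shift is under 2 points.

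A reader might also assume that every change of status moves the difference one-for-one, so that six of 80 patients suffice for significance (exact McNemar p = 2 × 0.5⁶ = 0.031). That requires no other discordant pairs. Two techniques at 85% with independent errors already give 2 × 0.85 × 0.15 × 80 = 20.4 discordant pairs. Six one-way pairs added to a 10/10 split give 16 against 10, exact p about 0.33.

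Finally, loss of isolation would work against the study's hypothesis rather than for it. That is true of this mechanism, but not of improving detectability.

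**Conclusion.** The point holds as a limited design weakness. Order and technique are inseparable in the comparison of ultrasound with auscultation, and nothing elsewhere in the protocol repairs this. Whether a material bias results is not known. The illustrated shifts of 1.4 to 7 points rest on assumed rates of change of 2% to 10%, equal accuracy of 85% and independent errors.

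The hypothesis that ultrasound is at least 80% accurate is not affected by its order relative to auscultation. It is exposed only to the age of the single FOB reference. The exploratory time comparison is not distorted by waiting, because the time for each study examination starts at first touch.

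The change is worth making because it is cheap and the analysis cannot recover the information afterwards.

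**What to change.** In section 6.3, replace the fixed sequence with an order randomised 1:1 (40 patients auscultation first, 40 ultrasound first), taken from a list or envelope opened once the drape is in place. Record the clock times of lung isolation, FOB confirmation and the start of each examination. In section 17.1, report the paired accuracy difference overall and, descriptively, by order. If the order cannot be changed, record the times and state the possible order effect as a limitation.

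The cost is an order list and a few recorded times. Both examiners are already in the room, so no patients, staff or procedures are added, and the sample size stays at 80. Gel must be wiped off before auscultation in half the patients. With 40 patients per order, the by-order results have low power and should not be read as a test for a period effect.

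The change does not make the FOB reference more recent. Nor does it settle two separate issues: whether the second examiner is kept unaware of the first result, and the difference in operator grade (section 6.1 allows a resident, CRNA or SRNA to auscultate, while section 5.1 requires a trained and experienced anesthesiologist for ultrasound).

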4.0 Study Endpoints

- 4.1 The accuracy of using ultrasound to assess lung isolation by visualizing lung movement or lack thereof of both the operative and non-operative lung fields.
- 4.2 Time to confirm lung isolation.

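### Does the missing start and stop event for bronchoscopy time undermine the secondary comparison of confirmation times?

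*Combined protocol and SAP*

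**What the plan says.** The secondary objective in section 2.1 is to "compare the time required to confirm lung isolation using the above-mentioned techniques including auscultation, FOB, and ultrasound". Section 4.2 lists the endpoint as "Time to confirm lung isolation", without an operational definition. Section 17.1 gives the analysis and its standing: "As a secondary, exploratory aim, we will compare the time to perform each of the techniques using paired t-tests or sign-rank tests".

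The measurements are described in section 6.0. In 6.2 the care team first listens to the chest: "Clinical confirmation of effective lung separation will include auscultation with documentation of absence of breath sounds on the operative side". No timing is attached to that step. Bronchoscopy comes next: "Following this, correct placement of the DLT will be confirmed using FOB. The time to perform FOB will be determined". Section 6.3 then begins "Once SLV device placement is confirmed by bronchoscopy", after which the airway is draped and the blinded examiners come in. Their clock is explicit: "Procedure time will be calculated from the time that the participant touches the patient to the completion of the examination (auscultation or ultrasonography". Section 17.1 fixes what bronchoscopy is for, "using FOB confirmation of one-lung isolation as the reference standard".

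**The concern.** A paired comparison of times is clean only if each time runs between comparable events. Here auscultation and ultrasound run from first touch to the end of the examination. FOB has no stated events, so its time could begin at scope pick-up or at insertion, and could end at the first adequate view, after an adjustment, or at scope removal.

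The stages differ too. FOB is timed while placement is being established, and the other two once it has been. If a malposition were found and corrected with the scope in place, only the FOB time could absorb the correction. Pairing removes variation between patients but not a systematic difference between clocks.

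At stake would be the two contrasts that involve FOB. Section 3.2 gives time as one of three reasons for wanting an alternative to bronchoscopy, so a difference produced by the clock, or hidden by it, would bear on that argument. Events that were never time-stamped could not be reconstructed at analysis.

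**Working it through.** **1. The three measurements side by side**

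| Technique | Start and stop | Stage | Source |
|---|---|---|---|
| FOB | Not stated; a time is to be recorded | At the confirmation step | 6.2 |
| Auscultation (study) | First touch to end of examination | After bronchoscopic confirmation | 6.3 |
| Ultrasound | First touch to end of examination | After bronchoscopic confirmation | 6.3 |

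Three techniques give 3 × 2 / 2 = 3 pairs. Two involve FOB. The third, ultrasound against auscultation, has one clock and one stage, so the gap does not reach it.

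**2. Does any planned figure depend on the FOB clock?**

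The only power statement is in section 12.2: more than 80% for accuracy with 80 patients. With 85% as the null value, 95% as the true value, and a two-sided 0.05 level (assumed, since alpha is not stated):

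- Standard error under the null: √(0.85 × 0.15 / 80) = 0.0399
- Standard error under the alternative: √(0.95 × 0.05 / 80) = 0.0244
- Power: Φ((0.10 − 1.96 × 0.0399) / 0.0244) = Φ(0.89) = 81.4%

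The stated figure reproduces on this reading. Other readings of the sentence give other values (85% true against a null of 75% gives 55.1%), but none uses a time. The documents give no standard deviation, effect size or power for time, so there is no planned time figure for the gap to disturb.

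**3. What an offset would do, if there were one (all inputs assumed)**

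For a constant offset of d standard deviations of the paired differences, 80 pairs, no true difference and two-sided 0.05, the rejection probability is about Φ(d√80 − 1.96) + Φ(−d√80 − 1.96), with √80 = 8.944.

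- d = 0.1: Φ(−1.066) + Φ(−2.854) = 0.145 (noncentral t: 0.143)
- d = 0.2: Φ(−0.171) + Φ(−3.749) = 0.432 (noncentral t: 0.424)

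Suppose instead that FOB time includes repositioning in a share of cases, with a standard deviation of 90 s before that is added. By simulation of the paired t-test:

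- 5% of cases at 60 s (mean offset 0.05 × 60 = 3 s): rejection 6%
- 10% at 120 s (mean offset 12 s): 19%
- 20% at 120 s (mean offset 24 s): 54%

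The result moves from negligible to large purely with the assumed share and duration, and the documents supply neither. The figures describe paired tests with 80 pairs in general and are not evidence about this trial.

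**4. What the text supports**

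Section 6.2 places FOB after the device is in and the lung is isolated, and asks for the time taken to perform it. The plain reading is the length of the bronchoscopic examination, which is close in kind to the 6.3 clock. No section mentions repositioning. The opening of 6.3 allows that the scope may stay in use until placement is right, but does not say that such time is counted.

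The order of the examinations follows from the design. FOB is the reference standard and must establish placement before blinded examiners are asked to judge it. Stating start and stop events would not remove that difference in stage.

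**The case for a change.** The strongest case is that this is a fact of the text and cheap to close. The parenthesis in 6.3 limits the clock to two techniques. First touch does not carry over neatly to a scope passed through an airway device already in place. Different staff could pick different events from case to case. A sentence or two and a pair of time stamps would settle it. Sections 1.0 and 2.1 also call the time comparison the secondary objective, and 4.2 makes it one of only two endpoints, so the exploratory label in 17.1 does not make it trivial.

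Much of this stands. The definition is absent, and nothing elsewhere supplies it. Anyone reporting the FOB contrasts should say what was timed.

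What does not stand is the step from a missing definition to a flawed analysis. Section 6.2 commits to recording a duration, and the documents do not show what the data form specifies, so loss of the needed time stamps is a possibility only.

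The one substantive alternative would be to test FOB time with any repositioning removed and report the inclusive time descriptively. That is a choice of estimand. With an endpoint framed as time to confirm isolation, time spent under the scope until isolation is confirmed has a fair claim to be included. Separating looking from adjusting may also be difficult in practice, and a difference in stage would remain.

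**Conclusion.** The observation is accurate but needs no change to the plan. It is missing operational detail that study staff and analysts can fill sensibly by taking FOB time as the duration of the bronchoscopic examination and saying so when reporting. Its reach is two of three contrasts in an aim that section 17.1 calls exploratory. The accuracy analysis, the sample size and the ultrasound-auscultation time contrast are unaffected.

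The size and direction of any offset are unknown, and the 6% to 54% range above rests wholly on assumed inputs. The conclusion assumes that FOB timing is done in a reasonably uniform way across cases. If the recorded times turned out to mix examination with correction, the two FOB contrasts would call for cautious interpretation, and the main result would still stand.
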